There are no specific treatments for the MPNs. The JAK1/2 inhibitor ruxolitinib is approved for the treatment of disease-related symptoms and splenomegaly in adult myelofibrosis (including PMF, PPV-MF and PET-MF) patients. It is effective at alleviating constitutional symptoms, normalizing blood counts and reducing spleen size in many patients. Ruxolitinib does not appear to significantly alter the natural history of the disease but mortality in a three year period is reduced 50% in the high-risk patients. Ruxolitinib is effective only during administration; symptoms recur soon after treatment is stopped. Fibrosis in the marrow is largely unaffected by treatment with ruxolitinib; there is no short-term clinical impact on *JAK2V617F* allele frequencies, but treatment for more than three years may reduce the allele burden (Deininger *et al.*, 2015).

Other treatments principally manage symptoms. Anaemia associated with an erythropoietin (EPO) level <100 mU/mL may respond to EPO therapy but is associated with an increase in hepatosplenomegaly. Prednisone can be effective for patients with evidence of active inflammation or autoimmune disease. Allopurinol is used to treat hyperuricaemia. Thalidomide at doses up to 100 mg/day in combination with prednisone improves anaemia and thrombocytopenia in approximately 60% of PMF patients and reduces spleen size in approximately 20% but is not approved for this indication in many countries. Low dose pegylated interferon- $\alpha$ 2a early in the course of the disease reduces splenomegaly and can produce molecular remissions but is associated with cytopenias and neurotoxicities but is not approved for this indication in many countries (Kiladjian *et al.*, 2008). Hydroxycarbamide has a low incidence of acute toxicity but also causes myeloid suppression. Low-dose alkylating agents can reduce organomegaly, reverse marrow fibrosis and improve blood counts but only occasionally has durable effects.

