#### 6.5 Guidelines

Patient safety is paramount. The guidelines provided below are intended to provide some consistency across sites by providing guidance to be used by the Investigator, the study staff and the patient to safeguard patient safety while maintaining data integrity. The guidelines are not intended to supersede best clinical judgment by the Investigator. Please contact the Medical Monitor with questions or with planned/known divergences from these guidelines.

1. In general, supportive care (transfusions, administration of anti-fungals, etc.) should be maintained in accordance with institutional policy. Additionally:
  - a. It is advised that patients with a platelet count  $\leq 10 \times 10^9/L$  (10 k/ $\mu L$ ) be transfused.
2. Hydroxyurea may be used during the study in case of proliferation as follows:
  - a. At the PI's discretion, initiate hydroxyurea treatment for white cell count  $\geq 30 \times 10^9/L$  (30,000/ $\mu L$ ) and majority of cells appear to be immature cells (myelocytes/ promyelocytes)
  - b. Discontinue hydroxyurea treatment when white cell count is  $< 10 \times 10^9/L$  (10,000/ $\mu L$ )
3. Patients taking medications that have the potential to induce or inhibit CYP3A4 or CYP2D6 should be monitored closely for potential effects of co-administration; particular attention should be given to anti-infectives in the azole class.
4. Cessation of IMG-7289 is invariably associated with a rebound in thrombopoiesis and the platelet count can easily exceed the baseline value in any given patient. When IMG-7289 is discontinued, the platelet count should be monitored closely and the timing of the start of an alternative therapy should take this into account.

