#### 6.6 Prohibited Medications

Please consult the Medical Monitor with any questions pertaining to prohibited medications.

1. All cytotoxic agents, with the exception of hydroxyurea
2. All haematopoietic growth factors: romiplostim, eltrombopag, granulocyte and granulocyte-macrophage colony stimulating factor (G-CSF and GM-CSF) and erythropoietin (EPO)
3. Prednisone and prednisolone  $> 10$  mg/day (noted exception: use of corticosteroids for management of gout is allowed) and dexamethasone  $> 4$  mg/day. Maintenance supplemental corticosteroid therapy such as prednisone  $\leq 10$  mg/day or corticosteroid equivalent is allowed.
4. Monoamine oxidase A and B inhibitors
5. Anticoagulant and nonsteroidal anti-inflammatory drug (NSAID; including aspirin) use are prohibited in patients when their platelet count is  $< 50 \times 10^9/L$  (50 k/ $\mu L$ )

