### **12.7 Pharmacodynamic Data**

Measuring the activity IMG-7289 has in producing a pharmacodynamics response (PD) is an exploratory objective. There are four PD responses of interest. The effect of the drug(s) on normal myeloid haematopoiesis, which will be measured by standard peripheral blood counts with on therapy. The PD effect on inflammatory cytokines and growth factors which will be measured regularly before and during the treatment period. The PD effect on the mutant allele burden of the patients-specific mutations identified at the time of enrollment and assessed in bone marrow cells (when accessible) and in peripheral blood at the end of the treatment period. The PD effect on the change in spleen volume by MRI and palpation. The PD effect on the change in bone marrow fibrosis score.

Chi-square ( $\chi^2$ ), Fisher exact, and Kruskal-Wallis tests may be used to assess the significance of differences in haematologic and pharmacodynamics markers among the patients and differing doses of IMG-7289. If applicable, progression free survival (PFS), event free survival (EFS), and overall survival (OS) will be calculated using the Kaplan-Meier method.

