VIII. Efficacy Analyses

A. Primary Analysis

1. Spleen Volume

Spleen volume (mL) will be measured by MRI (or CT scan where applicable) from Day 0. Descriptive statistics will be presented for actual spleen volume, change from baseline, and percentage change from baseline by visit; and for maximum percentage change from baseline, minimum percentage change from baseline, and best percentage change from baseline will be presented. The best percentage change from baseline is defined as the maximum percentage decrease or the minimum percentage increase if there is no decrease in a patient during treatment.

In addition, an analysis of mean spleen volume will be performed. The mean and its 95% confidence interval (CI) will be presented for the spleen volume (mL), change from baseline, and percentage change from baseline at each visit; and for the best percentage change from baseline. P-value for test to assess change from baseline at each visit will be calculated using paired t-test. P-value for test to assess percentage change from baseline at each visit and the best percentage change from baseline will be calculated using one sample t-test with the hypothesis that the percentage change is 0.

2. Spleen Size

Spleen size (cm) will be measured by palpation at each visit. Descriptive statistics will be presented for actual spleen size, change from baseline, and percentage change from baseline by visit; and for maximum percentage change from baseline, minimum percentage change from baseline, and best percentage change from baseline will be presented. The best percentage change from baseline is defined as the maximum percentage decrease or the minimum percentage increase if there is no decrease in a patient during treatment.

In addition, an analysis of mean spleen size will be performed. The mean and its 95% confidence interval (CI) will be presented for the spleen size (cm), change from baseline, and percentage change from baseline at each visit; and for the best percentage change from baseline. P-value for test to assess change from baseline at each visit will be calculated using paired t-test. P-value for test to assess percentage change from baseline at each visit and the best percentage change from baseline will be calculated using one sample t-test with the hypothesis that the percentage change is 0.

CCI

CCI

CCI

CCI

CCI

[figure not shown]

IX. Safety Analyses

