Sites are intended to document on the AE eCRF those events with an onset date on or after the date on which IMG-7289 was first dispensed, and within 28 days of last IMG-7289 treatment; therefore, all reported AEs are expected to be treatment-emergent. However, if eCRF completion guidelines change, or are not followed adequately, treatment-emergent events will be identified programmatically per the above definition, using imputed start date.

CCI

C. Clinical Laboratory Results

The following laboratory tests will be conducted:

- Complete blood counts (CBC) and differential
- Coagulation
- Chemistry panel including LFTs (AST, ALT, total bilirubin and alkaline phosphatase (ALP)) gamma glutamyltransferase (GGT), albumin , C-reactive protein), lactate dehydrogenase (LDH), uric acid. *Note that C-reactive protein was added starting with amendment 5.*
- Urinalysis with microscopy

Laboratory values will be listed and summarized at each assessment. Numerical laboratory results will be summarized for the actual values, change from baseline (CFB), and percentage CFB by visit; and for the maximum and minimum change from baseline. P-value for test to assess maximum and minimum change from baseline within each cohort will be calculated using paired t-test.

Shift tables for laboratory values with respect to normal range (low, normal, high) and CTCAE toxicity grade, compared to baseline, will be summarized by visit. Overall laboratory result shift from baseline (Normal, Abnormal clinically significant (CS), and Abnormal non-clinically significant (NSC)) will be summarized.

D. Vital Signs

Vital sign assessments will be summarized for the actual values, change from baseline, and percentage change from baseline by visit; and for the maximum and minimum change from baseline. P-value for test to assess maximum and minimum change from baseline within each cohort will be calculated using paired t-test.

E. Physical Examination

Physical exam data will be listed. Note that for Phase 2b patients, a limited version of physical exam data is collected.

F. Prior and Concomitant Medications

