Prior medication is defined as any medication with a stop date prior to the date of first dose of IMG-7289. Concomitant medications are defined as medications or therapies with a start date on or after the first dose of IMG-7289. Medications may be flagged as both prior and concomitant if the start date is prior to the date of the first dose of IMG-7289 and the medication continued after the first dose of IMG-7289. The medications will be coded using the most updated version of WHO Drug at the time of study initiation (up-versioning will not occur) and will be listed by cohort and by patient. The number (%) of patients using prior, prior and concomitant, and concomitant medications will be summarized.

G. Prior and Concomitant Transfusions

Prior transfusions are defined as those with a transfusion start date from the 15 days prior to Screening up to the first IMG-7289 dose. Concomitant transfusions are defined as those with a transfusion start date on or after the date of the first IMG-7289 dose. Prior and concomitant transfusions will be listed and summarized.

H. Prior and Concurrent Cancer Chemotherapy

Prior chemotherapy is defined as therapy that has ended before the first IMG-7289 dose. Concurrent cancer chemotherapy is defined as having a cancer chemotherapy start date on or after the date of the first IMG-7289 dose. Prior and concurrent chemotherapy will be listed.

X. Pharmacokinetic Analyses

Pharmacokinetic data are not within the scope of this SAP. Analysis details are provided in the protocol and in a separate Pharmacokinetic Analysis Plan.

XI. References

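### On-study hydroxyurea is permitted, but the SAP pools white-cell and spleen values from before and after it, so a patient who proliferates on IMG-7289 can be recorded with a white-cell fall

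*SAP*

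**What the plan says.** Protocol 6.5 (Guidelines) states: "Hydroxyurea may be used during the study in case of proliferation as follows". The investigator may "initiate hydroxyurea treatment for white cell count" of at least 30 × 10⁹/L when most cells look immature, and stops it once the count is below 10 × 10⁹/L. Protocol 6.6 prohibits "All cytotoxic agents, with the exception of hydroxyurea". Protocol 3.1, using the drug's other name, says: "Hydroxycarbamide has a low incidence of acute toxicity but also causes myeloid suppression".

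Inclusion criterion 10 requires previous therapies for the disease, chemotherapeutic agents among them, to have stopped at least 2 weeks before Day 0. SAP VI.B takes the last pre-dose assessment as baseline.

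SAP IX.C has laboratory results "summarized for the actual values, change from baseline (CFB), and percentage CFB by visit; and for the maximum and minimum change from baseline", with a paired t-test on the maximum and minimum change. SAP VIII.A.1 and VIII.A.2 give spleen volume and palpated size by visit, plus each patient's best percentage change during treatment. On the by-visit change they say: "P-value for test to assess change from baseline at each visit will be calculated using paired t-test".

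No readable general rule separates the data:

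- The Safety population is the only analysis set (VI.K).
- There is no covariate adjustment (VI.F).
- Missing safety data are carried forward (VI.C).
- Concomitant medications are listed and counted (IX.F). For chemotherapy, "Prior and concurrent chemotherapy will be listed" (IX.H). Neither is linked to the laboratory or spleen analyses.

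**The concern.** The primary objectives concern the effect of IMG-7289, with reduction in spleen volume among them. Protocol 12.7 names as its first pharmacodynamic response the effect "on normal myeloid haematopoiesis, which will be measured by standard peripheral blood counts". There is no control arm, so any change from an off-treatment baseline is naturally read as the study drug's.

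Hydroxyurea is a second myelosuppressive drug. It is started because white cells have risen on IMG-7289, and the white cell count is itself an analysed variable. When values from before and after the rescue are pooled, the later count reflects both drugs, and the summary cannot tell control by IMG-7289 from control by hydroxyurea. What is at stake is how white-cell results, and possibly spleen results, are interpreted. The choice of treatment for the patient is not in question.

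**Working it through.** **Plan's own figure.** There is none to reproduce. SAP IV.C gives about 75 treated patients and at least 45 completing the Initial Treatment Period, with no effect size or standard deviation for spleen or blood counts. The check needs neither number.

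**Inputs from the documents** (counts in 10⁹/L):

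- Start threshold 30, stop threshold below 10 (Protocol 6.5).
- Baseline free of prior therapy (inclusion criterion 10; SAP VI.B).
- Change is the value minus baseline, with all on-treatment values used (SAP IX.C).
- Entry sets no ceiling on the white cell count.

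**Single patient.** Let b be baseline, p ≥ 30 the count when hydroxyurea starts, and e < 10 the count when it stops.

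- Change before rescue = p − b ≥ 30 − b.
- Change after rescue = e − b < 10 − b.
- Fall over the course = p − e > 30 − 10 = 20, that is more than 20/30 = 66.7%.

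For b of at least 10 and below 30, the first change is positive and the second negative. With p = 30 and e = 9.9:

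| Baseline | Change before rescue | Change after rescue |
|---|---|---|
| 8 | +22.0 (+275%) | +1.9 (+23.8%) |
| 12 | +18.0 (+150%) | −2.1 (−17.5%) |
| 15 | +15.0 (+100%) | −5.1 (−34.0%) |
| 20 | +10.0 (+50%) | −10.1 (−50.5%) |
| 25 | +5.0 (+20%) | −15.1 (−60.4%) |

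Below a baseline of about 10 no fall is guaranteed, but the recorded rise shrinks.

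**Where this lands.** For the patient with baseline 20, IX.C reports a maximum change of +10.0 and a minimum of −10.1 (if no earlier value was lower). Both enter t-tests. The by-visit change after rescue is −10.1, and a missing later value may be filled by carrying it forward. Using only values before hydroxyurea, the last change is +10.0.

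**Cohort mean (illustration only).** If a share f of patients is rescued, the mean shifts by at least f × (−20): −1, −2 or −4 at f = 5%, 10% or 20%. Three things are assumed: the value of f; that every rescued patient is below 10 at the same visit; and that each would otherwise have stayed at 30 or more.

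**Spleen (illustration only).** If hydroxyurea added d percentage points of reduction, the mean would shift by f × d. With assumed values this runs from nothing (d = 0), through 5% × 10 = 0.5 points, to 20% × 35 = 7 points. No value of d is in the documents.

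**Neutrophils and platelets.** Protocol 3.1 implies extra suppression and gives no size. IX.C tabulates these counts as safety results, including shifts by CTCAE grade, so a hydroxyurea-related fall would appear as cytopenia on IMG-7289.

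**The case against.** The strongest reply is that IX.C is a safety section, and using every on-treatment value is a sound choice for safety. It makes no efficacy claim, and it does not hide the rise: the maximum change is reported and tested, by-visit tables and shift tables show the peak if it falls on a visit, and listings are planned. All of this stands. It means the planned summaries must be kept. It does not remove the misleading fall from the minimum change, its p-value or the later by-visit values.

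A reader might infer more than the documents support:

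- *That the bias favours IMG-7289 throughout.* It does so for white-cell control. For neutrophils and platelets in a safety table it runs the other way, and platelets are also the titration target (50–75 × 10⁹/L), so a platelet fall is not simply a good result.
- *That spleen results are inflated.* Protocol 3.1 credits other treatments with reducing spleen size or organomegaly. For this drug it mentions only low acute toxicity and myeloid suppression.
- *That cohort means shift by a known amount.* The rescue rate is not given, use is discretionary, and patients come off hydroxyurea below 10, so later values may be off it again.
- *That the plan has no rule anywhere.* The SAP text after VIII.A.2 and the protocol's exploratory endpoints are redacted. A rule for haematologic response may sit there. The point covers only IX.C, VIII.A.1 and VIII.A.2.

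The study is also not powered for significance statements on pharmacodynamic changes. The SAP nevertheless plans tests and intervals, and misattribution is not a matter of sample size.

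**Conclusion.** The gap is real and cheap to close. In the readable SAP, values before and after on-study hydroxyurea are pooled for white cells and for spleen volume and size. The firm consequence is conditional and concerns one patient: with a baseline white cell count between 10 and 30 × 10⁹/L, proliferation to the start threshold followed by a count below the stop threshold must be recorded as a fall, although the maximum change still shows the rise. This follows from the protocol's thresholds alone.

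The size at cohort level is unknown, because it depends on a rescue rate and a course without rescue that the documents do not give. For spleen, both the size and the existence of an effect are unknown, so that part is a gap in handling and not a demonstrated bias. For neutrophils and platelets, misattribution would count against IMG-7289.

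**What to change.** Amend SAP VIII.A.1, VIII.A.2 and IX.C before database lock:

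1. Keep all planned all-values summaries. For safety these remain the analysis, including the all-values minimum for neutrophils and platelets, so that no low count after hydroxyurea is dropped.
2. Beside them, add a supplementary row using only values before the first on-study hydroxyurea dose, for white cells (by-visit and minimum change) and for spleen volume and size (by-visit and best percentage change).
3. Report the number of patients who have started hydroxyurea by each visit.
4. Query partial hydroxyurea start dates, since SAP VI.D allows entries with only the year. Where a date stays partial, use the earliest possible on-study date for the split.
5. Base statements about IMG-7289's effect on both rows.

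The cost is SAP wording, some date queries and a few table rows; start and stop dates for concomitant medication and chemotherapy are already collected. The downside is that the supplementary row has fewer values and leaves out proliferating patients after rescue. It should therefore be read only with the all-values row and the rescue count. No change to the hydroxyurea guideline is proposed.

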Patients will be followed closely throughout the study for both Adverse Events (AEs) and signs of toxicity by frequent monitoring of clinical signs and symptoms and by peripheral blood and urine analyses. Pharmacodynamic effects will be closely monitored by frequent haematology assessments of peripheral blood, and requisite bone marrow aspirates and biopsies. Throughout dosing, transfusions may be administered if needed in accordance with standard institutional guidelines.

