#### **7.2.6 Interruption of Dosing**

Patients requiring a Dose Hold according to the Titration and Rechallenge Rules, or due to an (S)AE, should be monitored at least weekly for safety purposes and to enable re-challenge to commence as soon as counts return to the required level, if it safe to do so. During these visits, patients are required to undergo complete blood counts only.

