H. Interim Analyses and Data Safety Monitoring Committee (DSMC)

No formal interim analysis is planned for this study.

The DSMC reviews safety parameters and pharmacodynamic markers to draw conclusions around the safety and pharmacodynamic effect of IMG-7289. The DSMC responsibilities will remain in effect until study has ended.

The DSMC/SAB also reviews patient dose titrations and may recommend adjustments. At the original starting dose of 0.25 mg/kg/day, two sentinel patients were dosed for 7 days of treatment before initiating enrollment on a rolling basis. Data from the first sentinel patient was reviewed by the DSMC prior to dosing the second sentinel patient. The DSMC/SAB convened within 4 days post-completion of 7 days of treatment for each of the sentinel patients at the original D_s and determined that it was safe for each sentinel patient to continue dosing, and that it was safe for additional patients to begin treatment with IMG-7289.

Additionally, the DSMC convened post-completion of 7 days of treatment of the required three patients at the new starting dose of 0.5 mg/kg/day and determined:

the safety of the new 0.5 mg/kg/day starting dose, and the ITP Day 3 (mid-week) visit could be removed from the visit schedule.

The DSMC is scheduled to meet at least monthly during Phase 1/2a and quarterly during Phase 2b.

I. Multiple Comparisons

No control for the effect of multiple comparisons is planned.

J. Application of Visit Windows

In general, summaries will present the visits that are expected for each dose/cohort. Visits will be represented by treatment period (ITP or ATP) and day within period; for subjects that experience more than one ATP, each ATP will be treated separately (e.g. ATP1, ATP2). If a visit that is presented on a particular page is expected for some dose/cohorts but not others, then the summary will indicate “n/a” for the visits that are not expected for that particular dose/cohort.

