If sufficient patients within a phase and cohort have visits that are performed off-schedule, and there is concern that summary by designated visit within period will be misleading due to comparison of assessments that have not had comparable treatment duration within that period, then visit windowing may be utilized for data summarization. In that case, visit windows will be defined by establishing the expected schedule for the dose/cohort, and establishing boundaries for each window as the midpoint between the previous expected visit day and the next expected visit day. Assessments will be slotted for summarization according to the visit windows, rather than the visit designated in the eCRF. If more than one assessment occurs within a particular window, then the assessment closest to the expected visit day will be used. If more than one such assessment exists, then the assessment whose visit designation in EDC is closest to the expected visit designation will be used. If windowing is applied for a given type of assessment, this will be indicated in the footnote of the summary table and the corresponding listing, and the listing will indicate both the visit designation from EDC and the visit window in which the assessment is included.

This methodology may be applied to summaries of laboratory data, vital signs data, and/or symptom scores. As assessment schedules may differ for these assessments, windows may be parameter type-specific.

K. Analysis Populations

Only the Safety population will be considered as analysis population for performing the various analyses. All enrolled patients who received at least one dose of IMG-7289 will be included in the Safety population.

Patients having no post-baseline disease assessment will be defined as NE (not evaluable).

L. Subgroups of Analysis Populations

The summaries and listings will be separated by the starting dose, and type of disease within starting dose. Summaries will include an “All Patients” category for each starting dose, as well as an “All Patients” category for the entire set of patients in the analysis set.

Categories for starting dose are: Phase 1/2a - 0.25 mg/kg/d (amendments 1, 2 and 3); Phase 2b - 0.5 mg/kg/d (amendments 4, 5); and Phase 2b - 0.6 mg/kg/d (amendment 6).

Categories for type of disease are: primary myelofibrosis (PMF), post-polycythaemia vera myelofibrosis (PPV-MF), or post-essential thrombocythaemia myelofibrosis (PET-MF) within starting dose category.

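### In the readable SAP, laboratory values are CTCAE-graded only by visit, so no table counts the patients who ever reached Grade 3 or 4 on treatment

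*SAP*

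**What the plan says.** SAP IX.C plans shift tables for laboratory values by normal range and by grade: "CTCAE toxicity grade, compared to baseline, will be summarized by visit". SAP VI.J says which visits appear: "In general, summaries will present the visits that are expected for each dose/cohort". If many visits are off schedule, windowing may be used, and then "If more than one assessment occurs within a particular window, then the assessment closest to the expected visit day will be used". The scope of that option is discretionary: "This methodology may be applied to summaries of laboratory data, vital signs data, and/or symptom scores".

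SAP IX.C has three other laboratory outputs. Numerical results are summarised by visit "and for the maximum and minimum change from baseline". There is a shift that is not tied to a visit: "Overall laboratory result shift from baseline (Normal, Abnormal clinically significant (CS), and Abnormal non-clinically significant (NSC)) will be summarized". All values are also listed.

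The protocol creates blood counts outside the expected calendar. Patients on a dose hold "should be monitored at least weekly for safety purposes and to enable re-challenge to commence as soon as counts return" (Protocol 7.2.6), and those hold visits require blood counts only. Patients whose dose has not stabilised may continue weekly or bi-weekly haematology (Protocol 9.3.3, 9.3.4, 9.4.2). Unscheduled visits are allowed at any time (note to Table 4, Protocol 9).

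**The concern.** Protocol 8.2.1 expects doses that lower platelets and, to a lesser degree, neutrophils. The first safety question about such a drug is how many patients ever reached Grade 3 or Grade 4. A shift table by visit answers a different question, namely how many were at that grade on a given day. Brief low counts in different patients at different visits appear as small numbers in many columns and cannot be added up, because the table does not link patients across visits.

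The protocol also asks for extra counts when values are low, and the SAP does not say whether those counts enter any graded table. The report could then describe severe cytopenia on a primary endpoint without giving the proportion of patients who had it.

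**Working it through.** The plan gives no rate of severe cytopenia, so there is no figure to reproduce. The check is in four steps.

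**1. Expected calendar (Protocol 5.1.1 and 5.1.2).** The Initial Treatment Period has 8 weekly visits (Days 7 to 56), 4 bi-weekly visits (Days 70 to 112) and 2 monthly visits (Days 140 and 168): 8 + 4 + 2 = 14. Weekly counts over 168 days would be 168/7 = 24. Expected visits cover 14/24 = 58% of the weekly positions and leave 10 uncovered. Each Additional Treatment Period has 6 expected visits after its Day 0, so 6/24 = 25%, leaving 18 uncovered.

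**2. One dose hold traced through the SAP.** Suppose a hold is decided at Day 112. Weekly counts follow on Days 119, 126 and 133, before the next expected visit on Day 140.

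- Without windowing, none of the three is an expected visit.
- With windowing, and reading the boundaries as midpoints between neighbouring expected days, the Day 112 window runs from (98 + 112)/2 = 105 to (112 + 140)/2 = 126. The Day 140 window runs from 126 to (140 + 168)/2 = 154.
- The three extra counts lie 7, 14 and 7 days from the nearest expected day. The scheduled counts lie within the visit allowance of 2 days (Day 112) or 3 days (Day 140).
- The scheduled values are kept and the three hold values drop out, whatever they show.

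**3. What by-visit counts say about patients ever affected.** Let n_v be the number at Grade 3 or worse at visit v, and N the number ever at that grade at an expected visit. Then

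max(n_v) ≤ N ≤ min(number treated, sum of n_v).

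Take the planned 75 patients, all with a count at every visit, and assume n_v = 4 at each of 14 visits. The lower limit is 4 (4/75 = 5.3%). The upper limit is 4 × 14 = 56 (56/75 = 74.7%). The same by-visit table fits both ends. Adding off-schedule values can only raise the number ever affected or leave it unchanged.

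**4. Whether another output supplies the number.**

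| Output | CTCAE-graded | Per-patient extreme | Off-schedule values |
|---|---|---|---|
| Grade shift (IX.C) | Yes | No, by visit | Not stated; expected visits in general |
| Maximum and minimum change (IX.C) | No | Yes, as a change | Not stated |
| Overall normal / clinically significant / not significant shift (IX.C) | No | Not stated | Not stated |
| Laboratory listings | Not a summary | No | Recorded values are listed |
| AE tables (IX.B) | Yes | Yes, highest grade | Only if reported as an AE |

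The minimum change shows each patient's deepest fall, but a fall is not a grade and gives no count of patients at Grade 3 or 4. The AE tables come closest. However, Protocol 8.2.1 treats the drug's effects on myeloid cells as pharmacodynamic and not adverse, so a low count reaches those tables only when the investigator judges it clinically significant (Protocol 11.2 and 11.2.2).

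**The case against.** The strongest reply is that existing outputs already cover much of this. SAP VI.J says only that summaries in general show expected visits. IX.C also speaks of summarising values at each assessment. Clinically significant laboratory abnormalities must be recorded as AEs, significance includes anything that may alter care (which a dose hold does), and AEs are counted once per patient at the highest grade. The table shells are a separate document, and parts of SAP VIII and IX are redacted. All of this stands. It limits the claim to the readable text and makes the AE tables a partial backstop. It does not supply a laboratory-graded count of patients ever affected.

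Four stronger readings are tempting but not supported.

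- A reader might infer that the worst counts fall mostly at off-schedule visits. Titration is decided from haematology at every visit (Protocol 7.2.3, 9.3.2), so the count that triggers a hold is normally a scheduled one and is already in the by-visit table.
- A reader might size the gap by laying assumed short episodes over the visit calendar. Many such episodes fall where no blood is drawn. That measures the sampling schedule, and no table could recover those values.
- A reader might say that the maximum and minimum rows give only means. SAP VI and VI.M summarise continuous variables with standard deviation, median and range as well.
- Because "Throughout dosing, transfusions may be administered if needed in accordance with standard institutional guidelines" (Protocol 5.1), a reader might infer that post-transfusion values bias the changes towards zero. The SAP lists and summarises transfusions (IX.G) and is silent on later laboratory values. Patients on regular red-cell transfusions are eligible, so the baseline may itself follow a transfusion and the direction of bias is not established. A low count drawn at an expected visit before a transfusion is still graded. Leaving out post-transfusion values would selectively remove the most anaemic patients.

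**Conclusion.** The point holds in a limited form. The readable SAP has no summary of worst on-treatment CTCAE laboratory grade, and no rule that brings dose-hold, extra or unscheduled counts into a graded table. The direction is a matter of logic: in the same patients, the number at a grade at any one visit cannot exceed the number ever at that grade. The size is unknown, because the documents give no rate, duration or timing of severe cytopenia. The 4-to-56 range rests on an assumed 4 patients per visit and complete counts in 75 patients. It shows what the table leaves open and is not an estimate. The finding does not extend to the laboratory outputs as a whole, and the absence is established only for the text that can be read.

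**What to change.** In SAP IX.C, before database lock, add a shift from baseline to worst on-treatment CTCAE grade for platelets, absolute neutrophil count and haemoglobin. State that it uses all post-baseline on-treatment values, including unscheduled and dose-hold blood counts, and that the visit selection and windowing in VI.J do not apply to it. Define the interval that counts as on treatment. Report the number and percent of patients ever at Grade 3 and ever at Grade 4, by starting dose and overall. Keep the by-visit shift, which shows the time course. If the shells or redacted text already contain this table, a cross-reference is enough.

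The cost is SAP wording and one extra table set from data already collected, with no change to the protocol or to patient care. The downside for the sponsor is that reported rates of severe cytopenia will be higher than any by-visit table suggests.
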